Rationale: Studies indicate that increased HDNL is the primary cause of increased liver fat. Our preliminary data demonstrates that hepatic fat is 3 times elevated in girls with PCOS compared to weight similar controls. GLP-1 concentrations are lower in girls with PCOS and hepatic steatosis.

Methods: HDNL will be assessed in the fasted and fed state utilizing an acetate tracer in a subset of subjects. Rates of HDNL will be compared to measures of hepatic and adipose insulin sensitivity.

II. Background and Significance:

a) Overall background:

[figure not shown]
Polycystic Ovarian Syndrome (PCOS) affects 6-10% of U.S. women, with an estimated economic burden of \$4 billion, and is increasing in prevalence in parallel with the obesity epidemic^{1,2}. PCOS includes elevated androgens, and higher rates of insulin resistance (IR), type 2 diabetes (T2D), nonalcoholic fatty liver disease (NAFLD) and cardiovascular disease (CVD)³⁻⁶. The increasing rates of obesity-related PCOS are a major contributor to the earlier onset and rising incidence of T2D, NAFLD and CVD³⁻⁷. Current PCOS therapies are marginally efficacious, and one of them, oral contraceptives, may adversely affect CVD risk⁸⁻¹⁴. *Despite the high prevalence and serious morbidity associated with PCOS, a gap exists in the current therapeutic options.*

b) Mechanisms of insulin resistance in PCOS

Alterations in hepatic metabolism may be central to IR and cardiometabolic disease in PCOS.

An estimated 50-70% of obese women with PCOS have NAFLD, compared to 20-30% of obese women without PCOS^{7,15}. Furthermore, obese women with PCOS and NAFLD are more IR than those without NAFLD, indicating a link between NAFLD and worsening IR in PCOS⁴. Liver enzyme concentrations, as a marker of NAFLD, independently predict dysglycemia and T2D onset¹⁶, and a new NAFLD medication decreased dysglycemia¹⁷, arguing for a tight connection between glycemia and liver health. In obese non-PCOS youth, NAFLD correlates with adipose, hepatic and muscle IR, is worsened by fructose consumption, and reversed by weight

Figure 1: Proposed Mechanism of NAFLD in PCOS

Mechanisms influenced by hyperandrogenism and unique in PCOS vs. T2D are in grey. Items with an * will be studied in this grant. HDNL = hepatic de novo lipogenesis, VAT=visceral adipose tissue, FFA=free fatty acids, GLP-1=Glucagon Like Peptide

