MRI-assessed rates of hepatic steatosis even higher than in T2D girls (Figure 2B). Hepatic fat in PCOS girls is weakly associated to markers of overall lipolysis, but is more closely related to visceral adipose tissue (VAT) and plasma markers of hepatic *de novo* lipogenesis (FFA n7, Table 1). Further, during IV-induced hyperinsulinemia during the clamp, girls with PCOS have lower rates of carbohydrate oxidation than obese controls (0.013 ± 0.0001 vs. 0.017 ± 0.002 mmol/min/kg), indicating preferential storing of glucose as evidence of metabolic inflexibility. Finally, markers of CVD, including carotid plaque development and exercise tolerance are similar between PCOS and T2D, indicating that PCOS status may be a significant risk factor for CVD even in youth. In summary, in youth with PCOS, excess liver fat may relate to adipose IR, hepatic IR and metabolic inflexibility with increased *de novo* lipogenesis from carbohydrates. Targeting improved understanding of these pathologic processes in a physiologic model is a logical step for reducing progression of T2D, CVD and NAFLD in PCOS youth.

[figure not shown]
Preliminary data from oral glucose tolerance tests in girls with PCOS:

Obese girls with PCOS have high 2 hour oral glucose tolerance test (OGTT) glucose and insulin concentrations (Figure 3 A and B). Of note, the PCOS OGTT insulin concentrations are higher than those achieved during the clamp 245 ± 40 IU/ml). Despite the relative hyperinsulinemia, they have poor insulin secretion relative to IR, i.e. a lower OGTT-derived oral disposition index (oDI) vs. obese controls (Table 1) indicating the presence of both β -cell dysfunction and IR. Girls with PCOS and an oDI of <1 , an established risk for T2D³⁵, have half the insulin sensitivity vs. those with an oDI of >1 (5.3 ± 2.1 vs. 10.8 ± 0.8 mg/kg lean/min). Thus it may be that inadequate insulin secretion during an OGTT allows for persistent lipolysis and gluconeogenesis, which increases hepatic fat content and worsens muscle IR. GLP-1 and leptin, both hormones affected by oral ingestion, may be involved in this physiologic interplay, which is completely ignored with hyperinsulinemic clamp IV glucose delivery. The combination of isotope tracers and oral nutrient delivery is required to answer this critical question. This data is one of the primary reasons that we need to move to an oral model.

Pilot Data on Liver fat and Insulin

Resistance in youth with PCOS:

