Known obstructive sleep apnea or treatment with CPAP will not be an exclusion criteria, however, those individuals already utilizing CPAP at home will be requested to bring it for admission and use it during the WatchPAT study, so that we capture their typical home sleep patterns.

III. Research Methods

A. Outcome Measure(s):

Primary Outcome Measure(s): Insulin concentration suppressing 50% glucose Ra (IC₅₀ glucose Ra) during OGTT.

Secondary Outcome Measure(s): Hepatic PME/ATP ratio change after OG load, Glycerol Ra during OGTT, Hepatic fat fraction from MRI, Rate of hepatic de novo lipogenesis.

Likely contributors to above measures: Lipid/glucose markers:(fasting C-peptide and lipid panel, HbA1c); hepatic markers:(c-reactive protein, glucagon, GLP-1 and leptin at baseline, 5 min and 30 min post glucose load to asses change with OG, adiponectin, AST, ALT, GGT), sex-steroids:(DHEAS, free and total testosterone, sex hormone binding globulin, progesterone, estradiol); Body size and composition: (BMI, waist/hip ratio, DEXA, hepatic visceral fat via MRI³⁸⁻⁴¹), Whole body fat oxidation at rest and following glucose ingestion as measured with a metabolic cart; metformin, OCP, Physical activity/ diet:(accelerometer, activity survey (3DPAR); Food frequency survey).Questionnaires for presence of obstructive sleep apnea. Questionnaires for perceived mental strengths and difficulty (note there is no assessment of suicidality on this tool). Obstructive Sleep Apnea, to be assessed with an overnight sleep study via WatchPAT

B. Description of Population to be Enrolled:

60 obese adolescent females with PCOS will be studied compared to 20 obese non-PCOS controls. This is number of studies needed to be completed statistically, thus more subjects may be enrolled, to allow for screen failures and dropouts. Total enrollment will be up to 105 subjects.

Ethnic Categories	Gender		
	Females	Males	Total
Hispanic or Latino	27	0	27
Not Hispanic or Latino	78	0	78
Ethnic Categories: Total of All Subjects	105	0	105
Racial Categories			
American Indian/Alaska Native	3	0	3
Asian	4	0	4
Native Hawaiian or Other Pacific Islander	3	0	3
Black or African American	20	0	20
White	75	0	75
Racial Categories: Total of All Subjects*	105	0	105

Inclusion Criteria:

- 1) Female
- 2) Ages 12-21

- 3) Sedentary- less than 3 hours of moderate (jogging, swimming etc) exercise a week.

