Differences between the two primary groups (PCOS, controls) will be assessed with a t test or for non-normally distributed data a non-parametric test such as Mann-Whitney U. Secondary outcomes include a Pearson correlation test of potentially related variables followed by targeted multiple regression to assess the relationship between hepatic IR or hepatic fat and adipose IR, hepatic gluconeogenesis, VAT, carbohydrate oxidation, androgens, metformin or OPC use and presence of OSA. As an exploratory analysis, the four groups will also be compared using an ANOVA. We recognized that we may not be powered for these analyses, but the data will be used as hypothesis generating for future studies.

The rate of hepatic De Novo lipogenesis is a secondary outcome. Based on our preliminary data that plasma markers of hepatic De Novo lipogenesis are 40% greater in those with fatty liver disease and the use of a high carbohydrate and fructose drink to increase the differences between groups, 10 subjects in each group will be needed to detect a difference in hepatic De Novo lipogenesis^{21,49,52}. The rate of hepatic De Novo lipogenesis will be correlated with measures of hepatic and adipose IR and MRI measures of NAFLD.

Non-Isotope OGTT calculations: The Matsuda model of IR will be used, and B-cell function [insulinogenic index ($\Delta I30/\Delta G30$) and ($\Delta C30/\Delta G30$) and disposition index ($1/IFasting \times \Delta I30/\Delta G30$) and ($1/CFasting \times \Delta C30/\Delta G30$) will be calculated^{40,53-55}.

Proposed Mathematical Model of Glucose and Glycerol Dynamics: The differential equations-based isotope labeled oral glucose minimal model (OMM*)⁵⁶ will be adapted to describe glucose and glycerol dynamics present in the collected data. In OMM*, the oral glucose minimal model (OMM) is modified to account for labeled glucose oral data obtained with the inclusion of a stable isotope tracer. This refinement allows an estimate of insulin sensitivity which is unique in that it accounts for both stimulation of adipose and muscle glucose uptake and inhibition of hepatic glucose release. In OMM*, glucose concentration G and insulin action on glucose disposal X are governed by the following equations:

$$\begin{aligned}\frac{dG}{dt} &= -[S_G^* + X^*] \cdot G + \frac{R_a(\alpha, t)}{V^*} \\ \frac{dX^*}{dt} &= -p_2^* \cdot X^* + p_3^* \cdot [I - I_b]\end{aligned}$$

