Analysis of the sleep study: Respiratory parameters of interest (defined below) include arousals, apneas, hypopneas, low oxygen saturation time (SaO2T), hypercapnia time (CO2>50), and oxygen saturation nadir (SaO2N). The arousal index (AI) is the number of arousals and awakenings measured by a shift of EEG signal to > alpha range for more than 3 seconds, divided by total sleep hours as previously defined(57). Apnea is defined as an absence of airflow for two or more breath cycles. Hypopnea is a visible decrease in airflow by nasal pressure signal (or by thermistor when pressure signal was unavailable) and either an EEG arousal or a drop in oxygen saturation of 3% or greater. Mixed apnea is an obstructive apnea combined with a central (absent effort) apnea. The AHI is comprised of the obstructive, mixed, and hypopnea events divided by total sleep hours; central apneas (seen in normal children)) are not included in the AHI. Intermittent hypoxemia, even brief episodes of mild drops from the normal baseline, is hypothesized to be a possible cause of neuropsychological dysfunction. SaO2T is the time in minutes with oxyhemoglobin saturation less than 95% measured by pulse oximetry in order to detect mild intermittent desaturation, (not seen in normal children. SaO2N is the nadir of oxyhemoglobin saturation. Hypercapnia time (CO2>50) is time in minutes with an end-tidal CO2 level greater than 50 mm Hg. Carbon dioxide levels are generally not measured in adult sleep laboratories. The AHI in normal non-snoring children has been determined to be less than 1.0, with little hypercapnia (sleep time with CO2 > 50 mm Hg, reported to be < 10-20%. There are no established diagnostic criteria for mild, moderate, or severe sleep apnea in children. OSA in adults is defined by the AHI: the number of apnea or hypopnea (partial obstruction) events per hour. However, continuous partial obstruction is underestimated by these criteria, and is considered significant by the Pediatric Sleep Program. Therefore, normal participants with evidence of continuous partial obstruction not meeting adult criteria for OSA, an AHI >1, or hypercapnia > 10% of sleep time will be excluded. For

this protocol, mild OSA is defined as AHI 1–4, moderate OSA as AHI 5–10, and severe OSA as AHI greater than 10.

All measures will be adjusted for OSA status (yes/no) and/or severity of AHI.

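### The correlation and regression plan names no term for PCOS status, so associations pooled across the two diagnostic groups can be created or inflated by the group gap

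*Combined protocol and SAP*

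**What the plan says.** The Overall Project Statistical Plan (Section VII) compares PCOS girls with controls by a t test or a rank test. It then names a "Pearson correlation test of potentially related variables followed by targeted multiple regression" to relate "hepatic IR or hepatic fat and adipose IR, hepatic gluconeogenesis, VAT, carbohydrate oxidation, androgens, metformin or OPC use and presence of OSA". A later paragraph adds: "The rate of hepatic De Novo lipogenesis will be correlated with measures of hepatic and adipose IR and MRI measures of NAFLD".

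PCOS status is not in either list. Nothing in the protocol says that these analyses are run within diagnosis, stratified or done as partial correlations. The one blanket adjustment, at the end of the sleep-study analysis in Section VII, is for sleep apnea: "All measures will be adjusted for OSA status (yes/no) and/or severity of AHI". In Section VII, diagnosis is used for the two-group test, the exploratory four-group ANOVA and the matching to the clamp cohort, but not for the associations.

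Recruitment is by diagnosis. Section III.B states: "60 obese adolescent females with PCOS will be studied compared to 20 obese non-PCOS controls". The enrollment table in Section III.C gives 50+10+10 = 70 PCOS girls and 20 controls. The power statement uses 32 and 13.

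**The concern.** When two groups differ in mean on both variables, pooling them produces a correlation even if the variables are unrelated among girls with the same diagnosis. The protocol expects such differences. The Aim 3 rationale reports that "hepatic fat is 3 times elevated in girls with PCOS compared to weight similar controls". The Preliminary Studies report that "girls with PCOS have lower rates of carbohydrate oxidation than obese controls", and Table 1 there shows higher fasting FFA in PCOS. The power statement supposes a difference in IC50 as well.

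The associations carry weight in this study. The main hypothesis, Aim 3 and the expected results in Section VIII all concern how lipolysis, hepatic glucose release, lipogenesis and hepatic fat relate to one another. If the group gap drives or inflates a correlation, it repeats the between-group comparison and is not separate evidence of mechanism.

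**Working it through.** **The plan's own figures.** The plan gives no power or error figure for the associations. The nearest figure is 86% power for the primary comparison (13 controls, 32 PCOS, difference 35, two-tailed 0.05), stated without an SD. The SD of 39 for glucose IC50 comes from the equivalence paragraph of the same section. With SD 39 the power is 77.9% (normal) or 76.0% (t). An SD of about 34 to 35 returns 86%. This does not prove an error, and nothing below depends on it. Only the difference (35) and the SD (39) are used here.

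**Standardized gaps.**
- IC50: d1 = 35/39 = 0.90.
- Fasting FFA (Table 1): 523±37 with n = 19, and 629±22 with n = 38. The table does not define ±. Read as SE, the SDs are 37√19 = 161.3 and 22√38 = 135.6, pooled 144.5, so d = 106/144.5 = 0.73. Read as SD, d would be far larger (3.8). The smaller value is used.
- Hepatic fat: threefold, with no SD, so its gap is an assumption.

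**Induced correlation.** Let p be the PCOS share and q = p(1−p), with zero correlation within each group:

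r = q·d1·d2 / √[(1 + q·d1²)(1 + q·d2²)]

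The chance of p < 0.05 follows from Fisher's z: m = atanh(r)·√(n−3), and P = Φ(m − 1.96) + Φ(−m − 1.96).

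Example with 60+20 and 0.90 on both variables: q = 0.75 × 0.25 = 0.1875; r = 0.1510/1.1510 = 0.131; m = 0.132 × √77 = 1.16; P = 21%.

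| PCOS + control | d1, d2 | Induced r | Fisher z | Simulated |
|---|---|---|---|---|
| 70+20 | 0.90, 0.90 | 0.12 | 20.9% | 21.1% |
| 60+20 | 0.90, 0.90 | 0.13 | 21.2% | 21.7% |
| 32+13 | 0.90, 0.90 | 0.14 | 15.3% | 15.7% |
| 10+10 | 0.90, 0.90 | 0.17 | 10.7% | 10.7% |
| 70+20 | 0.90, 0.73 | 0.10 | 15.8% | 16.2% |

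The simulation used 12,000 datasets per row: independent normals plus a group shift. Adding a PCOS indicator brought every row back to 4.8% to 5.2%.

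**Range over the unknown second gap** (60+20, d1 = 0.90): d2 = 0.5 gives 10%, 1.5 gives 42% and 2.0 gives 56%, with r from 0.08 to 0.24. These values of d2 are assumptions.

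**Hepatic de novo lipogenesis (HDNL).** The acetate subset is smaller, and its size varies within the protocol. Section IV has 10 with and 10 without PCOS; Visit 3 has 30 and 10. At 0.90 on both variables, 30+10 gives 12.6%. The plasma marker FFA n7 (29±13 vs 45±15) gives d = 0.19 if ± is SE and 1.11 if ± is SD. Against the IC50 with 10+10, these give 5.3% and 13.2%. The HDNL effect may thus be close to nominal.

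**Regressions** (60+20, 0.90 on both variables). The model held androgens, metformin, OCP and sleep apnea. Assumptions: 10 girls on each drug, apnea in 40% regardless of group, and androgens unrelated to the other variables within group. The false-positive rate for the predictor was 14.9%, 10.0% and 7.3% at assumed androgen gaps of 1, 2 and 3 SD. With PCOS status added it was 4.9% to 5.2%.

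**The case against.** **Pooling is inferred.** The plan names relationships to assess. It does not give a closed list of covariates, and the regression is left open. The pilot text describes the relation of hepatic fat to lipolysis within PCOS girls and correlations within girls with type 2 diabetes, which suggests the investigators may analyse by diagnosis. This stands as a limit: the point is that handling of group is not stated. Pilot practice does not bind the plan, however, and followed as written the analyses mix the groups.

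**Androgens already stand in for PCOS.** Partly so. PCOS entry requires clinical hyperandrogenism or raised testosterone, and controls must lack clinical signs. But clinical signs alone suffice for entry, so measured androgens need not separate the groups fully. Metformin/OCP use marks only treated girls; in the enrollment table 50 of 70 PCOS girls are untreated and would be coded like controls. The Pearson step and the HDNL correlations have neither covariate.

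**The analyses are only hypothesis-generating.** That caveat directly follows the four-group ANOVA and may not extend to the associations, which are labelled secondary outcomes.

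**Adjustment may remove real pathway.** Section VIII expects hepatic fat excess to be driven by androgens, so conditioning on diagnosis changes the question for that term. This stands, and it is why the pooled estimate should be kept.

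**A reader might infer that the reported associations would be artefacts, or that error rates near 80% are expected.** The documents support neither. The induced correlation is about 0.1 to 0.2 in the settings tied to the protocol's figures, so mixing can make a weak association significant or inflate a real one, but cannot alone produce a strong one. Rates near 80% need a gap of about 1.5 SD on both variables, and no stated SD supports that. Nor is a gap documented for every listed variable: no figure comparing visceral fat in PCOS girls and controls is given.

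**Conclusion.** The concern holds in a limited form. As written, the association analyses state no PCOS term and no stratification, although the groups are recruited by diagnosis and expected to differ on IC50, hepatic fat, FFA and carbohydrate oxidation. If the groups are pooled, the nominal 5% Pearson test runs at about 16% to 21% for the main analyses and, at the same 0.9 SD gaps, about 11% to 13% for HDNL. The regressions run at about 7% to 15%.

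These sizes rest on the pooled reading, on zero within-group correlation, on the SD of 39 carried over from the equivalence paragraph, and on assumed gaps for the second variable and for androgens. The direction does not depend on the exact values; the size does. The t test for the primary outcome is unaffected. The change should be made, but the omission does not threaten the study's main comparison.

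**What to change.** In Section VII:

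1. Include PCOS status in each multiple regression.
2. For every planned correlation, including those with HDNL, report the within-PCOS estimate and the partial correlation adjusted for PCOS status beside the pooled one.
3. State that mechanistic conclusions rest on the within-group or adjusted estimates and that the pooled correlation is shown for description.
4. For the androgen question, report the model with and without the PCOS term, since the two answer different questions.

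No new data are needed. For a predictor with a 0.9 SD group gap in a 60+20 sample, the PCOS term raises the variance of its coefficient by a factor of about 1 + 0.1875 × 0.90² = 1.15, or about 7% on the standard error, before any gain from a smaller residual variance. For androgens the cost is larger: at an assumed 3 SD gap the factor is 1 + 0.1875 × 9 = 2.69, or about 64% on the standard error. That collinearity is the reason for item 4.
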